## **4 STUDY PROCEDURES**

**4.1 Screening/Baseline Visit procedures:** Families will be recruited from a community sample through a variety of means, including email listservs, in-person interactions with study personnel, social media posting to local parenting groups, and publicly posted flyers. Those wishing to learn more about the study will contact our project manager, who will conduct screening and enrollment for those wishing to participate in the study.

**4.2 Intervention/Treatment procedures (by visits):** Intervention families will receive approximately 4 hours of ASL and development specific content related to language and feeding during home visits and phone calls. The initial in-home session with families will focus on teaching ASL signs indicative of hunger, thirst, and satiety. A video and placemat of mealtime signs will be left with families at the completion of the first visit. The remaining sessions, in-home over the next 3 months and by phone monthly thereafter for 6 months total, will focus on reinforcing ASL signing in addition to focused education on particular aspects of language development (receptive language preceding expressive language and increasing intentional communication), feeding development (such as hunger and fullness cues, fear of new foods, the importance of repeated food exposures, variations in intake from meal-to-meal, and the propensity to reject bitter tastes [many vegetables]), and appropriate portion sizes and variety for healthy growth.

In person visit lesson schedule (monthly from baseline at 4-9 months of age):

Visit 1 (baseline: T1): Signing with infants

Visit 2: Infant communication and responsive feeding

Visit 3: Nutrition, portion sizes, and neophobia

Visit 4 (T2): Infant intentionality

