where the rest of data collection will take place to minimize participant reactivity. After ASL and knowledge content delivery by the parent educator (experimental group only), participants will then prepare for cardiac data monitoring and video-recording. The initial period of training by the parent educator should allow some time for mother and child to adjust to the presence of study staff in their home and recover from any physiological arousal or reactivity in response to them. Then, an ambulatory electrocardiogram (ECG) monitor will be placed on mother's and infant's chests in order to record RSA patterns throughout the observation. This single channel ECG waveform recorder (Actiwave Cardio; Camntech) will be connected to two disposable ECG electrodes (ConMed Neonatal/Pediatric Huggables) placed below the sternum and on the left side of the body (connected to each other by a short lead). The Actiwave Cardio monitors are flat, lightweight (<8 g), and comfortable with high levels of intra- and inter-instrument reliability as well as good validity of measures. Interbeat interval (IBI) data will be monitored and recorded for R-wave detection (providing an estimate of the degree of vagal influence on heart rate). RA's will instruct mothers on how to place 2 electrodes onto her chest and her infant's chest. After a brief test of the signal strength, the infant's length and weight (in clean dry diaper only) will be measured in triplicate, using a calibrated length board and digital scale. Given the much shorter duration of our proposed monitoring (~1 hour), we feel confident in our ability to capture RSA data in both mother and infant. Then, mothers and infants will be given a 5-minute break to relax in order to give them time for de-escalation after physical measurements. Next, infants will listen to soothing music while seated in a baby seat (or other arrangement recommended by mother; for example, if infant is more comfortable and less likely to become distressed on a blanket or in a crib, we will do this instead) and mothers will read a neutral magazine (gardening) for a 4-min baseline measurement. Monitors will be worn for the entirety of the visit and feeding events will be marked within the time-stamped data. Video-recording will begin after intervention (or usual care) delivery, with mothers asked to wait at least 10 minutes after the video-recording begins before feeding their child. They can then feed their child whenever they feel it is appropriate. One camera will focus on the mother's facial expressions and movements and the second camera will focus on the infant's facial expressions and movements. As long as the infant is stationary during feeding (in mother's lap, a highchair, or booster seat), the infant's videographer will focus the camera at the beginning of the recording and then step away from the camera to minimize intrusiveness. Both videographers will swivel the camera and use the digital zoom to follow mother or child throughout the observation. From this position, the videographers can use the digital viewfinder and be out of view from the feeding room if possible. Video-recording will last until 2 minutes after the child's last bite of food. We are currently testing and refining these data collection protocols. All other self-report data from questionnaires other than NDSR will be entered in the field using Research Electronic Data Capture (REDCap) through UNC-Chapel Hill CTSA. Within a week of T1, T2, and T3, two 24-hour recalls (to account for day-to-day variation) will be collected using NDS-R software by telephone five to 10 days apart. Twenty-four-hour recalls provide intake during a specified period, are open-ended, can accommodate various foods or food combinations, do not require literacy and have a relatively low respondent burden.

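### In the experimental arm only, lesson 1 comes before the T1 feeding video and RSA recording, so T1 is not a clean baseline for those outcomes; the primary outcome is not affected

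*Combined protocol and SAP*

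**What the plan says.** The lesson schedule in section 4.2, repeated in section 7, ties the first and last in-person lessons to measurement visits: "Visit 1 (baseline: T1): Signing with infants" and "Visit 4 (T2): Infant intentionality". On content, "The initial in-home session with families will focus on teaching ASL signs indicative of hunger, thirst, and satiety".

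Section 10 gives the order within a visit: "After ASL and knowledge content delivery by the parent educator (experimental group only), participants will then prepare for cardiac data monitoring and video-recording". It says so again for the video: "Video-recording will begin after intervention (or usual care) delivery, with mothers asked to wait at least 10 minutes". Length and weight come after the electrodes are placed: "After a brief test of the signal strength, the infant's length and weight (in clean dry diaper only) will be measured in triplicate". A 5-minute break and a 4-minute resting RSA recording follow in both arms. The lesson is also meant as acclimatisation: "The initial period of training by the parent educator should allow some time for mother and child to adjust" to the staff in the home.

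For diet, "Within a week of T1, T2, and T3, two 24-hour recalls (to account for day-to-day variation) will be collected", by telephone and 5 to 10 days apart. Section 4.3 lists these calls under follow-up procedures. Section 10 has the questionnaires entered in the field but does not say whether before or after the lesson.

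Section 6.3 allows two analyses: a test of the slope difference from baseline (the only model in the synopsis), or between-group contrasts at each visit. It also plans tests of change within each group, and lets variables that differ between arms at T1 be considered as covariates.

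**The concern.** A baseline is useful because treatment cannot have affected it. Here the experimental mother is taught hunger, thirst and satiety signs, and minutes later she is filmed feeding and scored on responsiveness to feeding cues. Controls have had no session. Any immediate response to the lesson becomes part of the T1 group difference.

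Three uses of T1 would then be affected. The slope test measures change from T1. The within-group tests do the same, and tertiary outcome A(1) is an improvement in observed responsiveness. The covariate rule in section 6.3 could take a lesson-induced T1 difference for chance imbalance and adjust it away.

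Measurement conditions also shift over time in one arm. A lesson precedes measurement at T1 and T2, but no in-person lesson is listed at T3. The T2 effect size, which section 6.3 wants for planning later studies, would mix a lesson given minutes before with any lasting effect. For RSA, the acclimatisation that the lesson provides is not available to controls.

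**Working it through.** **Which T1 measures follow lesson 1 in the experimental arm**

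| Measure | Outcome level | Position relative to lesson 1 | Could it have moved? |
|---|---|---|---|
| Weight-for-length Z | Primary | After | No, minutes only |
| Dietary recalls | Secondary | Probably after; a recall before the visit is not strictly excluded | Possibly |
| RCFCS (feeding video) | Tertiary | After | Possibly |
| Questionnaires | Tertiary and other | Not stated | Unknown |
| RSA | Exploratory | After | Possibly |

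**Inputs (section 6.4).** 32 complete dyads per arm, AR(1) correlation 0.9, difference of 0.4 SD by T3, one-sided 0.05, stated power above 0.86. The T1–T3 correlation is 0.9² = 0.81.

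**The plan's own figure.** If T1 means are taken as equal, the T3 variance given T1 is 1 − 0.81² = 0.3439. The SE is √(0.3439 × 2/32) = 0.1466, and power is 0.861 (normal approximation; 0.854 with noncentral t). A model with free T1 means, plus 8 further dyads per arm seen at T1 and T2 only, gives 0.866. The stated figure is reproduced. The first route assumes equal T1 means, which an immediate lesson effect would break.

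**What the slope test compares.** With three equally spaced visits and AR(1) correlation, the generalised least squares weights for the slope are (−1, 0, +1). With complete data the test is T3 minus T1, and T2 has no weight. Var(Y3 − Y1) = 2(1 − 0.81) = 0.38, so the SE is √(0.38 × 2/32) = 0.1541. Power for 0.4 SD is 0.829 (normal) or 0.822 (noncentral t, 62 df).

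**Effect of a T1 difference.** Let d be the between-group difference already present at T1, in the direction of the T3 effect. The change contrast estimates 0.4 − d. T3 adjusted for T1 estimates 0.4 − 0.81d. The values of d are assumptions.

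| d (SD) | T3 − T1 (SD) | Power, noncentral t | Power, normal | T3 adjusted for T1 (SD) | Power, normal |
|---|---|---|---|---|---|
| 0 | 0.40 | 0.822 | 0.829 | 0.400 | 0.861 |
| 0.1 | 0.30 | 0.610 | 0.619 | 0.319 | 0.702 |
| 0.2 | 0.20 | 0.359 | 0.364 | 0.238 | 0.491 |

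**The alternative in section 6.3.** The unadjusted T3 contrast still estimates 0.4 SD, with SE √(2/32) = 0.25. The ratio is 0.4/0.25 = 1.6 against a critical value of 1.645, so power is about 0.48. It avoids the attenuation by giving up the precision that T1 supplies.

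**The case against.** Much of the case on the other side stands. The primary outcome is untouched, and this is an early-stage study whose data collection procedures are, by section 10, still being refined. A reader might infer that the baseline is spoiled for the whole trial, or that both planned analyses subtract the effect. Neither follows. Weight and length do not respond within a visit, and the visit-wise contrast at T3 does not use T1 unless T1 is adjusted for.

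A reader might also infer a certain bias toward no effect. The documents give neither the size nor the sign of an immediate effect. Mothers learn the signs first and teach the infant afterwards, and responsive feeding is the topic of Visit 2. An effect in the opposite direction would inflate the slope contrast.

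For RSA, it is tempting to say that change scores differ by arm through acclimatisation alone. The documents support only that they may: both arms get the 5-minute break and the same quiet recording, and the planned RSA analysis is an association with feeding responsiveness, not a comparison of arms.

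For the recalls, the latest reading puts the second call at day 7 + 10 = 17 after lesson 1. That is one reading of an ambiguous window. Lesson 4 before the T2 measures has little bearing on hypotheses stated for T3.

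What remains is the order itself. It is stated twice without an exception for T1, and no analysis can recover a pre-lesson value that was never measured.

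**Conclusion.** The point holds for RCFCS and RSA, and probably for the T1 dietary recalls. It is possible but not shown for the questionnaires, and it does not apply to weight-for-length Z. The loss arises under the slope test, under within-group change and under adjustment for T1, and only if the lesson has an immediate effect in the direction of the T3 effect. The attenuation range rests on an assumed 0.1 to 0.2 SD at T1, together with the plan's correlation of 0.9, equally spaced visits and 32 complete dyads per arm. The unadjusted T3 contrast is not attenuated, but at about 0.48 power it is a weak fallback. Severity: should-fix for the secondary, tertiary and exploratory outcomes, before T1 data are collected.

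**What to change.** Change section 10 so that at T1 and T2, in both arms, the questionnaires, resting RSA and feeding video are completed before any lesson content, after one common settling-in period. Lesson content and the number of visits stay as they are.

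For the T1 recalls, obtain at least the first before lesson 1 where consent arrangements allow. This needs IRB agreement, because section 12 obtains consent by telephone beforehand but written consent only in the home, and adolescent mothers also need a guardian's permission. Requiring both recalls first would add their 5-to-10-day gap before lesson 1, which matters for infants near the upper age limit at first training. Where no recall can precede the lesson, do not treat the T1 recalls as pre-intervention and do not adjust for them as a baseline.

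The cost is small: a reordering within existing visits and, where possible, an earlier telephone call. The lesson would follow the meal, so some visits may run longer.

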## **11 RECRUITMENT STRATEGY**

Families will be recruited from a community sample through a variety of means, including email listservs, in-person interactions with study personnel, social media posting to local parenting groups, publicly posted flyers, posting on Craigslist, and contact through local church leaders. Those wishing to learn more about the study will contact our project manager, who will conduct screening and initial enrollment for those wishing to participate in the study. In the case of social media (a local parenting group on Facebook in this case), our rationale is accessing a local community of parents as potential participants in the study. [name] has permission from the moderator of this local parenting group to post information about the study to their group. The information would match what we have submitted to the IRB for consideration as the email to go out across the UNC listserv. We will designate that the posting is only to let families know about the study and that any questions should not be asked on the Facebook site, but instead directed to our project manager at her email or phone. No data will be collected through social media; it is purely informational to facilitate recruitment contact through email or phone directly to project manager. As [name] will be the one posting the announcement about the study within the group, he can respond to anyone who does pose questions on Facebook and direct them to contact our project manager rather than use Facebook. If possible, [name] will turn off the comment feature on the post to prevent disclosure of the identities of people interested in the study. In-person recruitment strategies include approaching caregivers with infants in waiting rooms of WIC clinics to ask if they are interested in learning about the study. Any conversation regarding the specifics of the study should be conducted in a private location. The onsite recruiter will notify subjects that their decision to participate in the study will not affect the care they receive at the clinic. To protect the privacy of potential subjects during recruitment, eligible and interested subjects will be screened in a private room. If a private room is unavailable, subjects will be screened and initially enrolled in the study via phone at a later date. Identification through local church leaders will be through church leaders' willingness to share information from our study flyer with their congregation.

Those wishing to learn more about the study will contact our project manager, who will conduct screening and initial enrollment for those wishing to participate in the study. Screening and initial enrollment occurs by telephone. Any contact information for individuals who decline to participate or are not eligible is immediately deleted from the contact database.

Potential subjects will be contacted through their preferred method, telephone or email. An initial email from the project manager, research assistant, or PI will include a question about whether our research team can leave a voicemail with a request for call back. If potential subjects choose to call rather than email and they are put through to voicemail, the voicemail will instruct them to answer the question about whether our research team can leave a voicemail with a request for call back. Contact information will be entered into a password protected contact database.

## **12 CONSENT PROCESS**

Subjects will be contacted by telephone prior to the home visit for data collection. During the telephone conversation, the study will be described and telephone consent to participate will be obtained. Once in the family home, the study will be described once more and written consent will be obtained.

We have put together a combined Adult Consent and Parental Permission form. Parents will be given the form for review on-site and study staff will go through the permission form verbally with the parent(s)

and offer to answer any questions prior to parental signature. If mothers of infants are adolescents, we will obtain their permission for their infant to participate, their assent to participate, and their parent or legal guardian's permission for them (the adolescent parent) to participate. We will have Spanish language versions of the Combined Adult Consent and Parental Permission forms for review in Spanish-speaking participants' homes. A bilingual research staff member on site will provide oral interpretation as needed.

### 13 PLANS FOR PUBLICATION

We plan to disseminate findings from primary, secondary, and tertiary outcomes through top-tier pediatric and nutrition journals.

